2.0 Specific Objectives

Objective 1: To characterize clinical outcomes, quality of life and functional impairment over two (2) years in a population of ambulatory patients on evidence-based therapy with advanced chronic systolic heart failure who may benefit from VAD therapy

- Characterize ambulatory patients with advanced heart failure at study entry, including measures of functional capacity and (baseline peak VO₂ and serial 6 minute walk test distance), frailty, biomarkers, and quality of life, and interest in VAD therapy.
- Characterize clinical outcomes of these heart failure subjects over two (2) years of follow-up, including a) hospitalizations, Mechanical Circulatory Support Device (MCSD) implant, heart transplant, survival without MCSD or transplant; survival without MCSD, transplant or substantially impaired health utility and b) functional capacity and quality of life.
- Develop improved risk prediction tools for use in this spectrum of advanced ambulatory chronic systolic heart failure.
- Determine if a second early assessment (at two months) of clinical information provides prognostic value that is additive to that of an initial assessment alone.
- Investigate the test performance characteristics of existing classification systems to determine: a) consistency of associated clinical characteristics of a given profile within

and between sites; b) performance metrics such as calibration, discrimination and accuracy; and c) prognostic ability with respect to clinical outcomes over time.

Objective 2: To evaluate the relationship between heart failure subject's modeled prognosis, self assessed prognosis, preferences for end of life care and thresholds for considering VAD implant.

Objective 3: To evaluate caregiver burden associated with heart failure subject's measures of heart failure severity, quality of life, functional limitations and with preferences for care and thresholds for considering device implant.

- Caregiver burden will be assessed at baseline B and again at 6 months, 1 year, 18 months and 2 years to explore its global trajectory, and as a function of each subject's heart failure severity, quality of life and functional limitations, and the caregiver's health status.
- Patient preferences for care and thresholds for considering device implant will be assessed as a function of caregiver burden.

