4.3 Maximal Oxygen Consumption (peak VO₂)

Maximal treadmill cardiopulmonary exercise tests (CPX) will be done for consented heart failure subjects at the baseline B visit. Maximal oxygen consumption (peak VO₂) during treadmill CPX is the most objective and well-validated measure of functional capacity.^[23] Its depression reflects the impaired ability to increase cardiac output and is an integrated measure of the cardiac, pulmonary, vascular and muscular abnormalities that characterize heart failure. While not completely effort-dependent, the adequacy of the effort as maximal can be determined.

The reliability of peak VO₂ measurement in the setting of stable outpatients with chronic heart failure has recently been assessed in 398 subjects participating in an HF-ACTION sub-study with test-retest measurements 1-2 weeks apart.^[24] The difference (mean \pm SD) in peak VO₂ measurement was 0.0±1.3 ml/min/kg (10th,90th percentile = 0.1,3.0) with nominal increases in 46% and decreases in 48% of subjects. This SD of 1.3 represented 9% of the mean peak VO₂ of these subjects. These data demonstrate the reproducibility of the peak VO₂ measurement and support the strategy of using a single measurement of peak VO₂ as an eligibility criterion in REVIVAL.

Maximal treadmill cardiopulmonary exercise testing is invaluable in the assessment of functional limitations imposed by heart failure and in predicting survival in patients referred for cardiac transplant evaluation. ^[19] [name] performed the landmark study demonstrating the utility of a peak VO₂ threshold of 14 ml/min/kg for selecting heart transplant candidates.^[25] At Columbia University, 396 patients age 65 years or older (mean + SD = 70±5) with systolic (80%) or diastolic heart failure (LVEF 30±15%, peak VO₂ 13.9±4.4 ml/min/kg) were followed until death (35%), urgent transplantation (8.8%), LVAD (3.0%) or elective transplantation (2.3%). Overall 1-year event-free survival was 81%. As seen in Figure 2, individuals with peak VO₂ 10-14 ml/min/kg and < 10 ml/min/kg had event-free survivals of ≈78% and ≈70% at 1-year and ≈60% and ≈45% at 2-years, respectively.^[26]

Figure 2: individuals with peak VO₂ 10-14 ml/min/kg and < 10 ml/min/kg had event-free survivals of \approx 78% and \approx 70% at 1-year and \approx 60% and \approx 45% at 2-years, respectively.

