4.13 Heart Failure Survival Score (HFSS)

The HFSS will be calculated by the Data Coordinating Center using data collected at baseline B. Instructions relevant to the calculation will be included in the MOP.

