4.17 Blood for Analysis, Specimen Handling and Storage

The REVIVE-IT Registry will bank samples for those heart failure subjects who consent to participate. From the developed sample bank the goals are to evaluate known biomarkers in this selected advanced heart failure sample and to develop novel biomarkers to improve the prediction of outcomes in subjects with advanced heart failure.

All heart failure subjects who consent to participate will have approximately 8 cc of blood collected for biomarker analysis at baseline B. Heart failure subjects who consent for the genomic analysis biomarkers will have an additional 13 cc collected at baseline B. These specimens will be shipped to the University of Pittsburg Biomarker Core Laboratory as specified in the MOP.

The final selection of biomarkers to be evaluated will be determined following an up to date review of the clinical literature as we approach the end of the study. The biomarkers are likely to include B-type natriuretic peptide, collagen markers (e.g., procollagen types I and III, n-terminal telopeptide, procollagen type I, c-terminal telopeptide, osteopontin, galectin-3), adiponectin, 8-isoprostane, IL-6, soluble receptor of type I alpha-TNF, ST-2, high-sensitivity CRP, CA-125 and troponin.

In addition, DNA banking and genomic analysis will be performed only for heart failure subjects with consent in place to permit the analysis. We will evaluate micro RNAs of prognostic interest in heart failure, such as miR-423-5p. We will genotype all consented heart failure subjects in REVIVAL for a core panel of 10 functional polymorphisms located in genes critical to heart failure progression including: ACE, aldosterone synthase, beta1 adrenergic receptor, alpha adrenergic receptor, NOS3, GNB3, corin (converting enzyme for BNP) and PDE5. At the completion of follow up, genomic analysis will be integrated with the clinical data set and outcomes compared by genotype. Given the role of these genes as targets for heart failure therapeutics, pharmacogenetic interactions will also be explored. In addition to the genotyping

of this core panel, DNA will be banked for analysis of future investigations of innovative genomic markers.

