8.3.3 Modeling of Clinical Outcomes

We seek to estimate the morbidity and mortality rates in this population and to evaluate the effectiveness of baseline factors in determining their prognosis. To accomplish this goal [objective 1], we will use logistic regression for dichotomous outcomes (e.g., proportion of subjects with an interest in VAD therapy), Poisson regression for count outcomes (e.g., number of hospitalizations per participant), Cox proportional hazard models for time-to-event outcomes (e.g., survival, time to VAD implantation) and linear mixed-effects models for continuous outcomes (e.g., quality of life, functional capacity)^[30-32]. For time-to-event outcomes, survival time will be defined as the time from consent to the event or, for participants who did not experience an event, to the last study visit. Given the potentially small number of events, differences between groups will be tested by means of the log rank test. For longitudinal continuous outcomes, we will model correlated errors with a first order autoregressive (AR1) process since it is reasonable to assume adjacent values are more correlated than observations father apart in time. Alternative variance-covariance structures will be investigated, if needed.

Univariable models will be developed first, using baseline characteristics as the predictors. Multivariable models will be built incorporating known prognostic factors (i.e., those identified in the literature) and those suggested from the univariable analyses (i.e., those with p<0.10). Given the sample size and the potential for small numbers of events (in time-to-event outcomes), we will apply the principle of parsimony to the number of potential prognostic factors included in the ultimate model. In addition to using such standard methods to develop multivariable risk prediction models, we will derive simplified scoring systems to aid in clinical decision-making. Alternative classification schemes (e.g., CART) will be employed as sensitivity analyses. To assess the performance of the risk prediction models, we will evaluate their calibration (or reliability) discrimination and accuracy^[33].

Comparison among existing classification systems and the use of second early assessments (baseline B measures instead of baseline A measures) with the improved risk prediction model(s) developed above will be based on the concordance index, parsimony of the model, and the other performance metrics described above^[34].

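### The test of a second early assessment in 8.3.3 is not limited to measures taken at both baseline visits, so a gain at baseline B can mix reassessment with newly added tests

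*Protocol*

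**What the plan says.** Objective 1 in section 2.0 sets the question: "Determine if a second early assessment (at two months) of clinical information provides prognostic value that is additive to that of an initial assessment alone". Section 8.3.3 turns it into a "Comparison among existing classification systems and the use of second early assessments (baseline B measures instead of baseline A measures", set against the improved risk models. The judgement "will be based on the concordance index, parsimony of the model, and the other performance metrics described above"; those metrics are calibration, discrimination and accuracy.

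The two visits do not carry the same battery. Exercise tests "will be done for consented heart failure subjects at the baseline B visit" (4.3). Section 4.13 states: "The HFSS will be calculated by the Data Coordinating Center using data collected at baseline B". Section 4.17 has "approximately 8 cc of blood collected for biomarker analysis at baseline B", and section 4.4 places the core-lab echocardiogram at the same visit. Sections 6.2.1 and 6.2.2 and Appendix A agree with this. The Seattle score, by contrast, is calculated at both visits (4.12), and the six-minute walk is done at both (4.2).

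**The concern.** Objective 1 asks about repetition: does a second look at two months add to the first? The contrast in 8.3.3 departs from that question in two ways.

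- It replaces A with B, whereas the objective asks what B adds to A.
- Nothing in it confines the B set to items that also exist at A. On the full sets, a better concordance at B could come wholly from exercise testing, echo or biomarkers done once. Adding B to A would not cure this, because the new tests would still enter only with B.

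The two explanations carry different messages. One supports bringing patients back at two months; the other supports a fuller work-up on a single occasion. The protocol's own text makes the new tests likely model candidates: it presents peak VO₂ and echo quantification as strong prognostic information, banks biomarkers to improve prediction, and builds multivariable models from prognostic factors known in the literature.

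**Working it through.** **1. Batteries side by side (6.2.1, 6.2.2, Appendix A, 4.12, 4.13)**

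| Measure | Baseline A | Baseline B |
|---|---|---|
| History, physical, NYHA, INTERMACS profile | yes | yes |
| ECG | yes | yes |
| CBC, metabolic panel, uric acid, cholesterol, INR | yes | yes |
| Grip, gait speed, six-minute walk | yes | yes |
| Quality-of-life, utility and preference questionnaires | yes | yes |
| Seattle score | yes | yes |
| Treadmill exercise test | no | yes |
| Heart Failure Survival Score | no | yes |
| Core-lab echocardiogram | no | yes |
| Biomarker sample | no | yes |

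Every clinical measure at A recurs at B. B adds three examinations and one score.

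**2. The protocol's own figures.** Section 8.2 gives only a precision statement. It reproduces: 400 × 0.70 = 280; 1.96 × √(0.05 × 0.95/280) = 2.55% and 1.96 × √(0.5 × 0.5/280) = 5.86%, which round to the stated 2.6% and 5.9%. It does not bear on the A-versus-B comparison, and the protocol gives no per-SD hazard ratios from which to size the problem.

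**3. A rough anchor for an effect size.** Section 4.3 reports 2-year event-free survival of about 60% for peak VO₂ of 10–14 and about 45% below 10. Under proportional hazards the ratio is ln(0.45)/ln(0.60) = 1.56. The 1-year figures (78% and 70%) give ln(0.70)/ln(0.78) = 1.44. These are unadjusted and compare strata, not standard deviations, so they only show that hazard ratios of the order used below are not far-fetched.

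**4. Illustration, first set-up.** Assumptions, none from the protocol except where noted:

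- one marker measured at both visits, HR 1.5 per SD, whose repeat carries no new information;
- one marker measured only at B;
- exponential event times with 30% events by 2 years (8.2 uses 30% for outcomes and drop-out together);
- 400,000 simulated subjects and true coefficients, so sampling error is negligible.

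Concordance is for event status at 2 years.

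| B-only HR per SD | Correlation with shared marker | A | All of B | Gain |
|---|---|---|---|---|
| 1.3 | 0 | 0.629 | 0.654 | 0.025 |
| 1.3 | 0.3 | 0.654 | 0.673 | 0.019 |
| 1.3 | 0.5 | 0.670 | 0.684 | 0.014 |
| 1.5 | 0 | 0.627 | 0.680 | 0.053 |
| 1.5 | 0.3 | 0.662 | 0.701 | 0.039 |
| 1.5 | 0.5 | 0.687 | 0.716 | 0.028 |
| 2.0 | 0 | 0.620 | 0.740 | 0.120 |
| 2.0 | 0.3 | 0.677 | 0.762 | 0.085 |
| 2.0 | 0.5 | 0.714 | 0.775 | 0.061 |

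Restricted to the marker taken at both visits, the gain is 0.000 throughout, which is the true value of the repeat in this set-up. (Gains were computed before rounding.)

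**5. Second set-up.** 400 subjects, 30% events by 24 months, shared score HR 1.6 per SD, survival c-index. For a B-only HR of 1.3, 1.5 and 2.0 the gain was about 0.02, 0.04 and 0.09 with an independent marker, and about 0.01, 0.02 and 0.05 at correlation 0.5.

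**6. Time origin.** Section 8.3.3 counts survival from consent, while B falls about two months later (±30 days). Subjects with B data have by design got through that interval. Restricting the variables is therefore not enough: unless both models use the same subjects and start the clock at B, they can differ in who is analysed as well as in what was measured.

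**The case against.** The best counter-argument is that replacement presupposes something to replace. Peak VO₂, echo and biomarkers have no A value, so the parenthesis can be read as a like-for-like swap of the repeated items, and an unseen SAP may say so. This stands as a reading, but no sentence in the protocol states it.

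Secondly, Objective 1 lists baseline peak VO₂ and biomarkers among study-entry characteristics, so these tests might sit in both models and cancel. That is possible, but the A model would then contain information gathered at two months and would no longer represent the initial assessment alone.

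Thirdly, the Heart Failure Survival Score is a calculation and may belong with the existing classification systems, and the final biomarker panel is chosen only near the end of the study. This narrows the list without emptying it: the exercise test and echo remain.

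Fourthly, the simulations assume the adverse reading and cannot show that the protocol requires it. This is accepted; they show only what would follow from it.

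Some subjects will have historic peak VO₂, survival-score or natriuretic peptide values from eligibility (5.1). These exist only for some subjects and are not part of the baseline A battery.

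A reader might infer that the second assessment is bound to look useful whenever any B-only test is prognostic. The documents do not support that. The like-for-like reading is open, parsimony and other metrics count beside concordance, and sampling error could hide a small gain.

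**Conclusion.** The point holds as a flaw in how the contrast is worded. Section 8.3.3 does not confine the comparison to measures common to both visits. If it is run on the full sets, a gain at B cannot be attributed to reassessment and is biased in favour of the second assessment. The replacement contrast also does not match the additive question in Objective 1. That the batteries differ is certain from the schedule; that the analysis will use the full sets is not. The size, about 0.01 to 0.1 in concordance, rests on assumed hazard ratios of 1.3 to 2.0 per SD for a B-only marker, correlations of 0 to 0.5, and a repeat with no information. It is an illustration and not a forecast. The matter deserves correction because it affects a stated aim of Objective 1 and the remedy is cheap.

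**What to change.** In 8.3.3:

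- Restrict the test of the second assessment to measures collected at both A and B: Seattle score, NYHA, INTERMACS profile, the common laboratory tests, ECG, six-minute walk, gait speed, grip and questionnaires.
- Compare A alone with A plus B, or with A plus the A-to-B change, so that the contrast answers the additive question.
- Fit both models in the same subjects, event-free and assessed at B, with time counted from B.
- Report the B-only tests as a separate step, shared measures against shared measures plus added tests, and label it as the value of added tests.

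The cost is a change of analysis wording and one further nested model, with no new data. The reported gain from the second assessment may be smaller, and events before B drop out of this one comparison. As a rough guide, if the whole of the protocol's 30% were events at a constant hazard, 400 × (1 − 0.70^(2/24)) ≈ 12 of 120 would fall before a visit at two months, and about 6 to 17 across the one-to-three-month window. Other analyses can keep consent as their origin.

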6.2 Study Procedures and Assessments

6.2.1 Baseline A

Initiation of baseline A will occur with the heart failure subject signing the Informed Consent document(s). Standard of Care (SOC) testing will be included in the heart failure subject evaluation for this visit. All SOC procedures are labeled as such below. All other procedures will be research expenses. After signing the informed consent document(s), subjects will undergo the following testing and evaluation:

- 1. Directed history and physical (including NYHA and INTERMACS Patient Profile)
- 2. ECG (SOC)
- 3. Blood draw for:
 - a. CBC with platelets and differential count [SOC]
 - b. Comprehensive metabolic panel [SOC]
 - c. Uric Acid
 - d. Total cholesterol
 - e. INR
- 4. Handgrip strength (by dynamometer)
- 5. Gait Speed Test
- 6. 6 minute walk test
- 7. Quality of life and health utility questionnaires
- 8. Patient preference questionnaire
- 9. Caregiver participation overview with heart failure subject
- 10. Dispense patient diary

If the heart failure subject has an historic ECG on file that was completed within 30 days of the assessment date, this may be used for fulfillment of this visit requirement if, in the opinion of the investigator, the historic ECG is highly likely to represent the subject's current health status.

If the heart failure subject has historic laboratory results on file that were drawn within 14 days of the assessment date, these results may be used for fulfillment of this visit requirement if, in the opinion of the investigator, the historic laboratory result(s) are highly likely to represent the subject's current health status.

Baseline A procedures should be completed within two weeks of consent. The baseline B visit should be scheduled to occur two (2) months (\pm 30 days) after consent.

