Model assumptions will be thoroughly checked using informal (e.g., inspection of residuals) and formal methods (e.g., score test for extra parameters or methods based on likelihood displacement). If individual outliers are detected, their influence will be evaluated using influence diagnostics methods based on comparing estimates from models fitted to data with and without outlying values. Whenever we are not successful in fitting the parametric models (linear or non-linear), then non-parametric analyses and/or transformation of the variables involved in the analysis will be considered.

Two-sided testing will be conducted using a nominal significance level of 0.05 for all tests. No adjustments for multiplicity will be applied. Further details of the analyses will be documented in the Statistical Analysis Plan.

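### Objective 1 asks what the two-month assessment adds to the initial one, but section 8.3.3 only replaces baseline A with baseline B, which does not estimate that increment

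*Protocol*

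**What the plan says.** Under Objective 1, Protocol section 2.0 lists this aim: "Determine if a second early assessment (at two months) of clinical information provides prognostic value that is additive to that of an initial assessment alone".

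Section 8.3.3 is the only place that says how the aim will be analysed. It compares existing classification systems, and "the use of second early assessments (baseline B measures instead of baseline A measures", with the newly developed risk model. It states that the comparison "will be based on the concordance index, parsimony of the model, and the other performance metrics described above".

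On model building, the same section says "Univariable models will be developed first, using baseline characteristics as the predictors". It does not say which baseline visit is meant. On timing, section 6.2.1 says "The baseline B visit should be scheduled to occur two (2) months" after consent, with a 30-day window either side, while section 8.3.3 says "survival time will be defined as the time from consent to the event".

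The protocol nowhere names a model containing both A and B measures, a term for the change from A to B, or a test of B given A.

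**The concern.** The objective and the analysis use different contrasts. An aim about value that is additive to the first assessment needs A plus B set against A alone. Using B instead of A asks which single visit predicts better. The two questions can have different answers: two imperfect readings of the same severity can predict equally well one at a time, yet better together.

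At stake is a named sub-aim. Baseline B repeats the history and physical, ECG, laboratory panel, walk test, grip strength, gait speed and questionnaires. If the written contrast were followed, a repeat that improves prediction could be reported as giving no gain. The protocol does not leave the contrast open for later: it states one, in a parenthesis, and that one does not match the aim.

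**Working it through.** **The plan's own figure.** The protocol gives no figure for this comparison. Its only design figure is the precision in section 8.2, with n = 400 × (1 − 0.30) = 280 and half-width 1.96 × √(p(1 − p)/n):

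- p = 0.05: 1.96 × √(0.05 × 0.95/280) = 0.0255 (stated 2.6%)
- p = 0.50: 1.96 × √(0.50 × 0.50/280) = 0.0586 (stated 5.9%)

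It reproduces, and the point here does not depend on it.

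**What each contrast can show.** Write c(A), c(B) and c(A+B) for the population c-index of correctly specified models on the same patients and variables.

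- Objective: c(A+B) − c(A).
- Section 8.3.3: c(B) − c(A).
- The joint model discriminates at least as well as either part, so c(A+B) ≥ c(B). If c(B) > c(A), then c(A+B) > c(A), and a win for B is evidence of added value.
- If c(B) ≤ c(A), c(A+B) − c(A) may be zero or positive. A tie or a loss for B does not settle the question.

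**Illustration 1: one stable trait read twice.** All inputs are assumptions, because the protocol gives none: severity U ~ N(0,1), A = U + e1, B = U + e2 with equal error variance, hazard proportional to exp(0.7U), 30% events by 24 months, N = 300,000.

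| Reliability of each reading | c(A) | c(B) | c(A+B) | B − A | (A+B) − A |
|---|---|---|---|---|---|
| 0.6 | 0.641 | 0.640 | 0.657 | −0.001 | 0.016 |
| 0.7 | 0.652 | 0.652 | 0.666 | 0.000 | 0.014 |
| 0.8 | 0.664 | 0.664 | 0.673 | 0.000 | 0.009 |

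Restricting to participants event-free at two months leaves the pattern unchanged.

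**Illustration 2: other relations between A and B.** Logistic model, N = 400,000, intercept −1.1, event rate 27% to 28%. The coefficients and the A–B correlation are again assumptions.

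| Scenario (coefficients of A, B; correlation) | c(A) | c(B) | c(A+B) | B − A | (A+B) − A |
|---|---|---|---|---|---|
| Equal effects (0.5, 0.5; 0.6) | 0.700 | 0.698 | 0.723 | −0.002 | 0.023 |
| Equal effects (0.5, 0.5; 0.8) | 0.721 | 0.721 | 0.733 | 0.000 | 0.012 |
| A stronger, B still adds (0.6, 0.35; 0.6) | 0.706 | 0.679 | 0.717 | −0.027 | 0.011 |
| Change matters (−0.5, 1.0; 0.7) | 0.553 | 0.668 | 0.692 | 0.115 | 0.139 |
| Only B informative (0, 0.8; 0.7) | 0.643 | 0.704 | 0.704 | 0.061 | 0.061 |
| Only A informative (0.8, 0; 0.7) | 0.705 | 0.642 | 0.705 | −0.063 | 0.000 |

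In the first three rows B adds information and the swap shows a tie or a loss. In the next two the swap shows most or all of the gain. In the last, B adds nothing and the swap shows a loss. A loss for B therefore occurs both when B adds something (row 3) and when it adds nothing (row 6), and the swap cannot tell these apart.

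**The case against.** The strongest case on the other side has five parts.

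- **A reader might infer that the swap can never show added value, or that a win for B shows only that recent data predict better.** Neither follows. A win for B on the same patients and variables implies that B holds information A lacks. What stands is narrower: the swap does not estimate the increment, and a tie or a loss is uninformative.
- **The equal-reliability illustration produces a tie by construction.** This is correct. It is one assumed scenario. Where change between visits matters, or only B is informative, replacement reveals much or all of the gain.
- **The 30% event rate is generous.** Section 8.2 counts drop-outs as well as clinical outcomes in its 30% and gives no split, so true events may be fewer. This affects the size and detectability of the gain, not the mismatch.
- **The gain is small for this study's size.** At n = 400 under the first illustration's model, a one-predictor likelihood-ratio test has power of about 0.6 to 0.8 at 30% events and 0.44 to 0.67 at an assumed 20%. A null result would still be common. The B − A difference in that setting, however, centres on zero with a standard deviation of 0.02 to 0.03, so it carries no signal about the increment.
- **This is an observational registry, and section 8.1 leaves further detail to the SAP.** The aim is one of several under one of five objectives, the analyses are described as descriptive or hypothesis-generating, and participant safety, enrolment and data collection do not depend on it. That lowers the severity. It does not cure a contrast that the protocol itself states as a replacement.

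**Conclusion.** The mismatch stands on the protocol's own words: the aim is value "provides prognostic value that is additive to that of an initial assessment alone", and the stated analysis replaces one assessment with the other. A joint model is not ruled out, but none is named.

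The consequence is one-sided. A win for B would be informative without measuring the increment; a tie or a loss would leave the aim unanswered and could be misread as no gain. Under the assumed stable-trait scenario, the gain missed is about 0.01 to 0.02 in c-index. That size rests on assumed reliabilities, effect sizes and event rate; the mismatch does not.

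This should be fixed, but it does not threaten the registry: measures repeated at both visits are already scheduled, so the contrast can be corrected at any time before analysis.

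**What to change.** In section 8.3.3, make the main contrast for this aim a pair of nested models: (1) A measures; (2) the same A measures plus their values at B or, equivalently for linear terms, the change from A to B. For this comparison:

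- Use only measures taken at both visits. Appendix A schedules the cardiopulmonary exercise test, echocardiogram, HFSS and biomarkers at baseline B only; including them would mix the value of repeating an assessment with the value of new tests.
- Restrict both models to participants event-free at baseline B and start survival time at that visit. B is measured about two months after the consent date from which time now runs.
- Test the added terms by likelihood ratio at the level already set in section 8.1 ("Two-sided testing will be conducted using a nominal significance level of 0.05 for all tests"), and report the change in optimism-corrected c-index and in calibration.
- Keep the comparison of B with A as a secondary description.

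The cost is a wording change and a few extra model fits on data already planned. There are two real drawbacks. The larger model spends more parameters, so the repeated measures must be few and chosen in advance to respect the section's parsimony rule. Participants with an event before baseline B also drop out of this comparison, though not out of the registry's other analyses.
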